### **4.8.1. Data Monitoring Committee (DMC)**

NA.

## **4.9. Changes to Protocol-Planned Analyses**

NA.

## 5. Sample Size Determination

Approximately 732 participants will be screened to achieve 585 participants randomly assigned in a 2:1 ratio to dulaglutide 1.5 mg group and dulaglutide 0.75 mg group (390 and 195 participants, respectively). Assuming a drop-out rate of 10%, 528 participants will be evaluable for an estimated total of 352 evaluable participants in the dulaglutide 1.5 mg group and 176 evaluable participants in the dulaglutide 0.75 mg group.

This sample size provides at least 90% power for demonstrating superiority of dulaglutide 1.5 mg to dulaglutide 0.75 mg in the HbA1c change from baseline at Week 26. This assumes a true treatment difference of -0.3% with a common standard deviation (SD) of 1.0% for the change in HbA1c from baseline.

For participants taking DPP-4i prior to randomization, target numbers of participants randomized for 1.5 mg and 0.75 mg are 150 and 75 (total 225 participants).

For participants taking other OAMs, target numbers of participants randomized for 1.5 mg and 0.75 mg are 240 (40 per OAM class) and 120 (20 per OAM class). In total, 360 participants (60 per OAM class) will be randomized for other OAMs.

## 6. Supporting Documentation

### 6.1. Appendix 1: Description and Derivation of Efficacy and Health Outcome Endpoints

**Table GBGQ.6.1. Description and Derivation of Efficacy/Health Outcome Measures and Endpoints**

Measure	Description	Variable	Derivation/Comment	Imputation Approach if Missing Components (postbaseline visit)
HbA1c		Continuous HbA1c (%) and mmol/mol	Observed score and change from baseline	Missing if baseline or observed value is missing.
HbA1c		Categorical HbA1c (%) value: Value <= 6.5% Value < 7.0%	Postbaseline	Missing if baseline or observed value is missing.
FSG		FSG (mg/dL and mmol/L)	Observed score and change from baseline	Missing if baseline or observed value is missing.
Body weight		Body weight (kg)	Observed score and change from baseline	Missing if baseline or observed value is missing.
6-point SMBG		Use (mg/dL) [A1] Pre-Morning Meal BG [A2] Morning Meal 2-hr PPBG [A3] Pre-Midday Meal BG [A4] Midday Meal 2-hr PPBG [A5] Pre-Evening Meal BG [A6] Evening Meal 2-hr PPBG	Observed score and change from baseline	Missing if baseline or observed value is missing.
6-point SMBG		Use (mg/dL) [B1] Morning pre meal to 2-hr excursion [B2] Midday pre meal to 2-hr excursion [B3] Evening pre meal to 2-hr excursion	Observed score and change from baseline [B1] = [A2]-[A1] [B2] = [A4]-[A3] [B3] = [A6]-[A5]	Missing if baseline or observed value is missing.

Measure	Description	Variable	Derivation/Comment	Imputation Approach if Missing Components (postbaseline visit)
6-point SMBG		Use (mg/dL) [C1] Mean of all pre meals to 2-hr excursion [C2] Mean of all 6-point BG [C3] Mean of all pre-meals BG [C4] Mean of all postprandial meals BG	[C1] = Average([B1], [B2], [B3]) [C2] = Average([A1], [A2], [A3], [A4], [A5], [A6]) [C3] = Average([A1], [A3], [A5]) [C4] = Average([A2], [A4], [A6])	When taking average, use non-missing values and take their average. If all values are missing, then the mean is considered as "missing." If baseline or observed value is "missing," then it is missing. E.g., If [A5] is missing, then [C3] = Average([A1], [A3])
6-point SMBG		Use (mg/dL) Daily Circadian Variation in 6-point BG	Observed score and change from baseline Max([A1], [A2], [A3], [A4], [A5], [A6]) - Min([A1], [A2], [A3], [A4], [A5], [A6])	Missing if all [A1]-[A6] are missing. When taking max or min, use non-missing values.

Abbreviations: BG = blood glucose; FSG = fasting serum glucose; HbA1c = hemoglobin A1c; PPBG = postprandial blood glucose; SMBG = self-monitored blood glucose.

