6-point SMBG values			X				X					6-point SMBG consists of measurements before and 2 hours after each of 3 main meals within the same day. These SMBG profiles will be collected by the participant twice (2 days) within 1 week prior to the assigned visits.
Dispense study intervention and/or injection supplies			X		X	X	X					
Injection training			X									All training should be repeated as needed to ensure participant compliance.
Observe participants inject study intervention			X									Participants should administer their first dose of study intervention at the end of this visit, after other study procedures and randomization.
Participants return study intervention and/or injection supplies					X	X	X	X	X			
Assess study intervention compliance					X	X	X	X	X			
Human chorionic gonadotropin (hCG)	X											Human chorionic gonadotropin (hCG) will be measured at Visit 1 for women of childbearing potential.
Follicle-stimulating hormone (FSH)	X											Follicle-stimulating hormone (FSH) will be measured at Visit 1 for potentially postmenopausal women.
Urine pregnancy test (local)			X		X	X	X	X	X			A local urine pregnancy test will be performed at Visit 3, with the result available prior to randomization and first injection of study intervention, and at additional visits as shown in the schedule, for women of childbearing potential only.
Hematology	X		X				X		X	X	X	
Clinical Chemistry	X		X				X		X	X	X	

	Screening/ Lead-In		Treatment Period							Safety Follow- Up	Comments	
			Treatment Period I				Treatment Period II					
Visit	1	2	3	4	5	6	7	8	9	ET	801	
Week of Treatment	-2	-1	0	2	8	16	26	38	52	ET	56	
Allowable Deviation (Days)	-7~+3	±3		±3	±7	±7	±7	±7	±7		±7	The visit date is determined in relation to the date of the randomization visit (± the allowed visit window).
Lipid panel	X		X				X		X	X	X	
Pancreatic amylase, lipase	X		X				X		X	X	X	
Calcitonin	X		X				X		X	X	X	
Urine chemistry	X		X				X		X	X	X	Urinary albumin and creatinine will be measured.
Urine albumin -to creatinine ratio (UACR)	X		X				X		X	X	X	
eGFR	X		X				X		X	X	X	eGFR: Calculated by the Japanese Society of Nephrology equation
Fasting serum glucose			X		X	X	X	X	X	X		
HbA1c	X		X		X	X	X	X	X	X		
Samples for storage			X				X		X	X		Plasma and serum stored samples. Additional samples may be collected at additional timepoints where required (in the event of severe hypersensitivity reactions such as anaphylaxis). See Section 8.3.3(f) and 8.9.

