#### **Baseline definition**

Baseline will be defined as the last available value before the first injection for efficacy. In most cases, this will be the measure recorded at Baseline Visit 3 (Week 0). If the participant does not take any injection, the last available value on or prior to randomization date will be used. Change from baseline will be calculated as the visit value of interest minus the baseline value.

For the safety analyses, the following baselines will be used. For safety analyses using a baseline period, the baseline period is defined as the time from Screening Visit (Visit 1) to the date/time of the first injection.

- Treatment-emergent adverse events (TEAEs): baseline will be all results (including medical histories which are ongoing at the date of informed consent) recorded during the baseline period.
- Treatment-emergent abnormal laboratory and vital signs results: baseline will be all results recorded during the baseline period.
- Change from baseline to last post-baseline observation or to each scheduled post-baseline visit for laboratory and vital signs results: baseline will be the last scheduled non-missing assessment recorded during the baseline period.

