#### **[Case 1] Single post-baseline time point (e.g., 6-point SMBG at Week 26, Lab analysis from baseline through Week 26)**

Change from baseline will be analyzed using analysis of covariance (ANCOVA) with the following terms in the model:

- treatment group, baseline value, pre-study OAM class, and baseline HbA1c stratum.

Type III tests for least squares (LS) means will be used for **statistical comparison between treatment groups**. The LS mean difference, standard error (SE), p-value, and 95% CI, unless otherwise specified, will also be reported. In addition, **within treatment comparison** (the post-baseline value v.s. baseline value) will be conducted with the same model. P-value will be reported.

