## 6.2. Appendix 2: Description of Efficacy and Health Outcome Analyses

Table GBGQ.6.2. Description of Efficacy and Health Outcome Analyses

Measure	Variable	Estimand (Section 1.1.1)	Analysis Method (Section 4.1)	Analysis Set (Section 3)	Comparison/Time Point	Analysis Type
HbA1c	Change from baseline	Primary Estimand (Hypothetical)	MMRM	ITT	DULA1.5 vs DULA0.75. Interim: Week 8, 16, 26 Final: Week 8, 16, 26, 38, 52	Week 26: primary analysis:  Other weeks: secondary analysis
HbA1c	Proportion of participants achieving HbA1c target of $\leq 6.5\%$ and $< 7.0\%$	Hypothetical	GLM	ITT	DULA1.5 vs DULA0.75. Interim: Week 8, 16, 26 Final: Week 8, 16, 26, 38, 52	Secondary analysis
FSG	Change from baseline	Primary Estimand (Hypothetical)	MMRM	ITT	DULA1.5 vs DULA0.75. Interim: Week 8, 16, 26 Final: Week 8, 16, 26, 38, 52	Secondary analysis
Body weight	Change from baseline	Primary Estimand (Hypothetical)	MMRM	ITT	DULA1.5 vs DULA0.75. Interim: Week 8, 16, 26 Final: Week 8, 16, 26, 38, 52	Secondary analysis

Measure	Variable	Estimand (Section 1.1.1)	Analysis Method (Section 4.1)	Analysis Set (Section 3)	Comparison/Time Point	Analysis Type
6-point SMBG	Change from baseline: [A1] Pre-Morning Meal BG [A2] Morning Meal 2-hr PPBG [A3] Pre-Midday Meal BG [A4] Midday Meal 2-hr PPBG [A5] Pre-Evening Meal BG [A6] Evening Meal 2-hr PPBG [B1] Morning pre meal to 2-hr excursion [B2] Midday pre meal to 2-hr excursion [B3] Evening pre meal to 2-hr excursion [C1] Mean of all pre meals to 2-hr excursion [C2] Mean of all 6-point BG [C3] Mean of all pre-meals BG [C4] Mean of all postprandial meals BG	Hypothetical	ANCOVA	ITT	DULA1.5 vs DULA0.75. Interim: Week 26 Final: Week 26 (No data at Week 52)	Secondary analysis
6-point SMBG	Change from baseline: Circadian Variation in 6-point BG	Hypothetical	ANCOVA	ITT	DULA1.5 vs DULA0.75. Interim: Week 26 Final: Week 26 (No data at Week 52)	Secondary analysis

Abbreviations: ANCOVA = analysis of covariance; BG = blood glucose; DULA0.75 = Dulaglutide 0.75 mg arm; DULA1.5 = Dulaglutide 1.5 mg arm; FSG = fasting serum glucose; GLM= generalized linear model; HbA1c = hemoglobin A1c; ITT = Intention-to-treat population; MMRM = mixed-effects model for repeated measures; PPBG = postprandial blood glucose; SMBG = self-monitored blood glucose.

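### Minor, secondary glucose-profile variables only: [C2] and circadian variation use whatever readings exist, with no pre-/post-meal balance or minimum count, and the order for combining the two profile days is not stated

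*SAP*

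**What the plan says.** SAP Table GBGQ.6.1 (Section 6.1) labels the six readings [A1] to [A6], pre-meal and 2-hour post-meal alternating. Three features matter here.

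- **Circadian variation.** The variable, named "Daily Circadian Variation in 6-point BG", is the maximum minus the minimum of [A1] to [A6]. Its missing-data rule is "Missing if all [A1]-[A6] are missing. When taking max or min, use non-missing values".
- **Means.** [C2] averages all six readings, [C3] the three pre-meal readings and [C4] the three post-meal readings. For all of them the rule is "When taking average, use non-missing values and take their average". The table's own example averages the two readings that remain.
- **Two days per visit.** Protocol 1.3 schedules the profile at Visit 3 and Visit 7 (Week 26) and states: "These SMBG profiles will be collected by the participant twice (2 days) within 1 week prior to the assigned visits". The table does not mention the two days. The efficacy baseline definition in SAP 4.1, "Baseline will be defined as the last available value before the first injection for efficacy", does not settle how they are combined.

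SAP Table GBGQ.6.2 lists [C2] and "Change from baseline: Circadian Variation in 6-point BG" as secondary analyses by ANCOVA at Week 26. SAP 4.1, Case 1, adds a within-treatment p-value against baseline to the between-arm comparison.

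**The concern.** A maximum minus a minimum depends on how many values go into it. Taking readings away from a given set can leave the range unchanged or lower it, but cannot raise it, and one reading gives exactly 0. The stated rule accepts any non-empty set.

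[C2] has a different weakness. Post-meal glucose is normally higher than pre-meal glucose, so a mean over available readings falls when post-meal readings are lost and rises when pre-meal readings are lost. [C3] and [C4] each average one type of reading and do not have this mixing problem.

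The two profile days add an undefined step. Averaging each time point over the days and then taking the range gives a different quantity from taking a range per day and averaging the ranges. Two programmers could follow the table correctly and report different values, even with no missing data.

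At stake are secondary estimates and their p-values. Last observation carried forward (SAP 4.1.2.1.2) does not help, because Week 26 is the only scheduled post-baseline profile and the table already deals with lost readings by using the rest.

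**Working it through.** The plan gives no SMBG figure to reproduce. Taken from the documents: the formulas above, two days per visit, and 352 and 176 planned evaluable participants. **Assumed**, because the documents give no SMBG mean, SD or completeness rate: pre-meal means 150/140/150 and post-meal means 210/205/215 mg/dL, SD 25 per reading (range 20 to 30), and independent random loss. Ranges were simulated.

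**1. Range by number of readings.** For independent normal readings with a common mean, the expected range in SD units for 1 to 6 readings is 0, 1.13, 1.69, 2.06, 2.33, 2.53. Five readings give 2.33/2.53 = 92% of the full range, three give 67% and two give 45%.

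**2. [C2], by hand.**
- Complete: (150 + 140 + 150 + 210 + 205 + 215)/6 = 1070/6 = 178.3.
- One post-meal time point missing: 865/5 = 173.0, 860/5 = 172.0 or 855/5 = 171.0, a shift of −5.3 to −7.3. If it is lost on only one of two days and daily means are averaged, the shift is half that, −2.7 to −3.7.
- Mean of [C3] and [C4]: complete, (146.7 + 210.0)/2 = 178.3. With one post-meal time point missing, [C4] is 212.5, 210.0 or 207.5, so the result is 179.6, 178.3 or 177.1, within 1.3 of the complete value.
- Simulated arm difference when post-meal loss is 15% in one arm and 5% in the other: −2.1 (per day), −0.4 (days averaged first), 0.0 (mean of [C3] and [C4]).

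**3. Day order and circadian variation** (mg/dL, SD 25, current available-readings rule).

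| Random loss | Range per day, then averaged | Days averaged first, then range |
|---|---|---|
| 0% | 106.9 | 94.7 |
| 5% | 104.6 | 95.8 |
| 10% | 102.1 | 96.7 |
| 20% | 96.3 | 97.5 |

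With SD 20 to 30, the complete-data values are 98 to 116 per day and 89 to 100 averaged first. The shift at 10% loss is about −5 per day and +2 averaged first. The upward shift arises because a time point resting on one day's reading is noisier than a two-day mean, which widens the range.

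**4. Within-arm test, no true change, 5% loss at baseline and 10% at Week 26** (paired test, normal approximation, two-sided 0.05).
- Per day: spurious change 102.1 − 104.6 = −2.5. With an SD of change of about 28, the standard error is 28/√352 = 1.49 and z = 1.68, so the false-positive rate is about 39%. For 176 it is about 22%. The simulation gave 38% and 21%.
- Averaged first: spurious change 96.7 − 95.8 = +0.9. The simulated rates are 9% and 7%.
- With 5% loss at both visits, the rate is 5% under either order.

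**5. Between arms, no true difference.** Equal random loss gives 0. With 5% loss in one arm and 10% or 20% in the other, the difference is 102.1 − 104.6 = −2.5 or 96.3 − 104.6 = −8.3 per day, and +0.9 or +1.7 averaged first.

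**The case against.** The strongest reply is that the range is probably not meant per day. Table GBGQ.6.1 gives each of [A1] to [A6] its own observed value and change from baseline, and Table GBGQ.6.2 analyses each by ANCOVA, so each must be one value per participant and visit. Read that way, the days are combined before the range is taken. If they are combined by averaging, the shift is small and upward. Only the word Daily in the variable's name points the other way, and Table GBGQ.6.2 drops it. This stands: a reader might infer that lost readings always make circadian variation too low, and the documents do not support that as a general statement.

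A reader might also infer that the dose comparison is biased. The same rule applies to both arms, and equal random loss leaves that comparison unbiased. A third tempting inference is that incomplete baseline profiles are handled differently, because the rule's column heading mentions only the post-baseline visit. The [C1] to [C4] cell under that heading refers to a missing baseline value too, and nothing indicates a second formula.

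It can further be said that using available readings is a disclosed, pre-specified choice, that the separate table, figure and listing specification (SAP Section 1) may hold a day rule, and that every mg/dL figure is assumed. All of that is fair. It does not remove two features of the stated rule: a profile with one reading counts as zero variation, and [C2] moves with the type of reading lost.

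**Conclusion.** The point holds as a minor one, confined to secondary SMBG variables. Two parts need no assumed glucose values: circadian variation has no minimum count, so sparse profiles tend to be understated and a single reading scores 0; and the two-day order is not stated in either document. That [C2] shifts with unequal pre- and post-meal loss needs only that the two types of reading differ in level.

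The sizes rest on the assumed profile, SD and random loss. On those values the order alone is worth about 12 mg/dL with complete data (95 or 107) and decides the direction of the shift under loss. The extreme case is rare: at 10% loss a single-reading day has probability 6 × 0.1⁵ × 0.9 = 0.005%. The within-arm p-value is distorted only if completeness differs between visits, and the high rates in step 4 also need per-day derivation. The 1.5 mg versus 0.75 mg comparison is affected only if completeness differs by arm or depends on glucose. The primary HbA1c analysis is not involved. The actual bias cannot be derived from the documents.

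**What to change.** Amend SAP Table GBGQ.6.1:

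1. Compute [C2] as the mean of [C3] and [C4], missing if either is missing. Complete profiles are unchanged.
2. Set circadian variation to missing when the profile has fewer than a pre-specified minimum of the six time points, with a complete-profile sensitivity analysis. The threshold is the sponsor's choice.
3. State one order for combining the two days and apply it to all SMBG variables at baseline and Week 26. Averaging each time point over the days first fits the visit-level use of [A1] to [A6] and is less sensitive to random loss. If the separate display specification already holds a rule, copy it into the table.

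**Cost.** Wording and derivation code, no new data. Some participants with sparse profiles lose a value. With days averaged first and random loss of 10% per reading, a time point is missing with probability q = 0.1² = 1%. With a minimum of five time points, as an illustration, the share without a value at one visit is 1 − 0.99⁶ − 6 × 0.01 × 0.99⁵ = 0.15%, or about 0.3% at either visit. Requiring all six gives 1 − 0.99⁶ = 5.9% and about 11.4%. The new [C2] is lost only if all six pre-meal or all six post-meal readings over the two days are missing, about 2 × 0.1⁶ per visit.

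**Limits.** A minimum count guards against sparse profiles. It does not remove the small upward shift from averaging days first, so the sensitivity analysis should define a complete profile. Taking the range per day from days with all six readings removes the shift under random loss, but leaves 13.5% (5% loss) or 39.1% (10% loss) of participants without a value at one or both visits. No threshold fully repairs glucose-dependent loss: with 30% of readings above 220 mg/dL lost and 3% of the others, the per-day value is 99.7 under the current rule and 103.4 with all six required, against a true 106.8.

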## 6.2. Appendix 2: Description of Efficacy and Health Outcome Analyses

Table GBGQ.6.2. Description of Efficacy and Health Outcome Analyses

Measure	Variable	Estimand (Section 1.1.1)	Analysis Method (Section 4.1)	Analysis Set (Section 3)	Comparison/Time Point	Analysis Type
HbA1c	Change from baseline	Primary Estimand (Hypothetical)	MMRM	ITT	DULA1.5 vs DULA0.75. Interim: Week 8, 16, 26 Final: Week 8, 16, 26, 38, 52	Week 26: primary analysis:  Other weeks: secondary analysis
HbA1c	Proportion of participants achieving HbA1c target of $\leq 6.5\%$ and $< 7.0\%$	Hypothetical	GLM	ITT	DULA1.5 vs DULA0.75. Interim: Week 8, 16, 26 Final: Week 8, 16, 26, 38, 52	Secondary analysis
FSG	Change from baseline	Primary Estimand (Hypothetical)	MMRM	ITT	DULA1.5 vs DULA0.75. Interim: Week 8, 16, 26 Final: Week 8, 16, 26, 38, 52	Secondary analysis
Body weight	Change from baseline	Primary Estimand (Hypothetical)	MMRM	ITT	DULA1.5 vs DULA0.75. Interim: Week 8, 16, 26 Final: Week 8, 16, 26, 38, 52	Secondary analysis

Measure	Variable	Estimand (Section 1.1.1)	Analysis Method (Section 4.1)	Analysis Set (Section 3)	Comparison/Time Point	Analysis Type
6-point SMBG	Change from baseline: [A1] Pre-Morning Meal BG [A2] Morning Meal 2-hr PPBG [A3] Pre-Midday Meal BG [A4] Midday Meal 2-hr PPBG [A5] Pre-Evening Meal BG [A6] Evening Meal 2-hr PPBG [B1] Morning pre meal to 2-hr excursion [B2] Midday pre meal to 2-hr excursion [B3] Evening pre meal to 2-hr excursion [C1] Mean of all pre meals to 2-hr excursion [C2] Mean of all 6-point BG [C3] Mean of all pre-meals BG [C4] Mean of all postprandial meals BG	Hypothetical	ANCOVA	ITT	DULA1.5 vs DULA0.75. Interim: Week 26 Final: Week 26 (No data at Week 52)	Secondary analysis
6-point SMBG	Change from baseline: Circadian Variation in 6-point BG	Hypothetical	ANCOVA	ITT	DULA1.5 vs DULA0.75. Interim: Week 26 Final: Week 26 (No data at Week 52)	Secondary analysis

Abbreviations: ANCOVA = analysis of covariance; BG = blood glucose; DULA0.75 = Dulaglutide 0.75 mg arm; DULA1.5 = Dulaglutide 1.5 mg arm; FSG = fasting serum glucose; GLM= generalized linear model; HbA1c = hemoglobin A1c; ITT = Intention-to-treat population; MMRM = mixed-effects model for repeated measures; PPBG = postprandial blood glucose; SMBG = self-monitored blood glucose.

### 6.3. Appendix 3: Demographic and Baseline Characteristics

Participant demographic variables and baseline characteristics will be summarized (All Randomized population). The continuous variables will be summarized using descriptive statistics and the categorical variables will be summarized using frequency counts and percentages. No formal statistical comparisons will be made between treatment groups unless otherwise specified.

The following demographic information will be included:

- Age/Sex/Race/Country
- Body Weight (kg) / Height (cm) / BMI
- HbA1c (%, mmol/mol)
- HbA1c Category (Low/High defined as stratification factor in [Table GBGQ.1.3](#), value < 8.5, 8.5 <= value, value < 9.0, 9.0 <= value)
- Fasting Blood Glucose (mg/dL, mmol/L) (show mean/SD/median/ min/max)
- eGFR Group (Stage G1/G2/G3a/G3b/G4/G5)
- Duration of Diabetes (years) (show mean/SD/median/ min/max)
- Duration of Diabetes (< Median, >= Median)
- Duration of Diabetes (< 5 years, >= 5 to < 10 years, >= 10 years)
- Systolic BP (mm Hg)/ Diastolic BP (mm Hg)/ Pulse (bpm)
- Age subgroup 1 (years) (2 groups: value < 65, 65 <= value)
- Age subgroup 2 (years) (3 groups: value < 65, 65 <= value < 75, 75 <= value)
- Body Weight (kg) (2 groups: value < median, median <= value)
- Baseline BMI (2 groups: value < 25, 25 <= value)

By-participant listings of basic demographic information will be provided.

